12.4.3 Laboratory Results

Laboratory test results will be collected pretreatment and on day 1 of each treatment cycle until the TD visit. Standard reference ranges will be used for missing or discrepant normal ranges.

Mean change from baseline in laboratory test values at each visit will be provided. On-study laboratory test abnormalities will be summarized. Shifts in laboratory test values will also be summarized.

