9. Women of childbearing potential must agree and commit to the use of a highly effective method of contraception, as determined to be acceptable by the Investigator, from the time of informed consent until 28 days after the last dose of the investigational products. Men must agree and commit to use a barrier method of contraception while on treatment and for 3 months after last dose of investigational products.
10. Provide written, informed consent to participate in the study and follow the study procedures.

Exclusion Criteria

1. Received previous therapy with capecitabine, neratinib, lapatinib, or any other HER2-directed tyrosine kinase inhibitor.
2. Received prior therapy resulting in a cumulative epirubicin dose >900 mg/m² or cumulative doxorubicin dose >450 mg/m². If another anthracycline or more than one anthracycline has been used, the cumulative dose must not exceed the equivalent of 450 mg/m² doxorubicin.
3. Any major surgery ≤28 days prior to the initiation of investigational products, or received anti-cancer therapy (including chemotherapy, biological therapy, hormonal therapy, investigational agents, or other anti-cancer therapy) administered ≤21 days prior to the initiation of investigational products.
4. Received radiation therapy ≤14 days prior to initiation of investigational products.
5. Symptomatic or unstable brain metastases. (Note: Asymptomatic patients with metastatic brain disease who have been on a stable dose of corticosteroids for treatment of brain metastases for at least 14 days prior to randomization are eligible to participate in the study).
6. Active uncontrolled cardiac disease, including cardiomyopathy, congestive heart failure (New York Heart Association functional classification of ≥2), unstable angina, myocardial infarction within 12 months of enrollment, or ventricular arrhythmia.
7. QTc interval >0.450 seconds or known history of QTc prolongation or Torsades de Pointes.
8. Screening laboratory assessments outside the following limits:

Laboratory endpoint	Required limit for exclusion
Absolute neutrophil count (ANC)	<1500/μL (<1.5 x 10 ⁹ /L)
Platelet count	<100,000/μL (<100 x 10 ⁹ /L)
Hemoglobin (Hb)	<8 g/dL (transfusions allowed) Transfusions must be at least 14 days prior to randomization.
Total bilirubin	>1.5 x institutional upper limit of normal (ULN)
Aspartate aminotransferase (AST) and/or Alanine aminotransferase (ALT)	>3 x institutional ULN (>5 x ULN if liver metastases are present)

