13.1.2 Abnormal Laboratory Results

The criteria for determining whether an abnormal laboratory test result should be reported as an AE are as follows:

- Test result is associated with accompanying symptoms, and/or,

- Test result requires additional diagnostic testing or medical/surgical intervention (merely repeating an abnormal test, in the absence of any of the above conditions, does not meet criteria for reporting and an AE), and/or
- Test result leads to a change in study dosing or discontinuation from the study, significant additional concomitant drug treatment or other therapy, and/or
- Test result leads to any of the outcomes included in the definition of a SAE, and/or,
- Test result is considered to be an AE by the Investigator or by the Sponsor

Any abnormal test result that is determined to be an error does not require reporting as an AE, even if it did meet one of the above criteria except for when the test result leads to any of the outcomes included in the definition of a SAE. Clinically significant laboratory results must be recorded in the patient's CRF.

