Grade 3 ALT (>5-20 x ULN) or Grade 3 bilirubin (>3-10 x ULN)	
 • Hold neratinib and capecitabine until recovery to Grade ≤1 for patients with ALT Grade ≤1 at baseline OR Grade ≤2 for patients with Grade 2 ALT at baseline. • Evaluate alternative causes. • For patients with ALT Grade ≤1 at baseline: resume at a reduced doses of neratinib 160 mg and capecitabine at 1100 mg/m² (550 mg/m² BID)^a if recovery to Grade ≤1 occurs within 3 weeks. If Grade 3 ALT or bilirubin occurs again despite the above-mentioned dose reduction, permanently discontinue neratinib and capecitabine. • For patients with Grade 2 ALT at baseline due to liver metastases: contact the Sponsor for guidance on appropriate dose adjustments.
Grade 4 ALT (>20 x ULN) or Grade 4 Bilirubin (>10 x ULN)	
 • Permanently discontinue neratinib and capecitabine. • Evaluate alternative causes.

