9.4. Clinical Laboratory Evaluation

Blood samples for clinical chemistry and hematology will be collected during screening, before study drug administration, on day 1 of each treatment cycle and at the treatment discontinuation visit. Samples for pregnancy test and urinalysis will be collected at screening and before study drug administration.

Laboratory data will be summarized in tables using descriptive statistics for baseline and each cycle/visit. Descriptive statistics will be calculated on both the actual score and the change from baseline score. Additionally, clinically significant abnormalities in laboratory results will be summarized for the post-baseline cycles/visits using frequencies and percentages. Shifts in normal/abnormal status between baseline and subsequent visits will be summarized as well.

The institutional laboratory will analyze all hematology, routine blood chemistry, and urine samples collected.

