	Diarrhea Characteristics
	Summary of Time to First Diarrhea Treatment Emergent Adverse Event by Severity
	Summary of Diarrhea Treatment Emergent Adverse Events Leading to Treatment Discontinuation
	Summary of Diarrhea Treatment Emergent Adverse Events Leading to Dose Hold
	Summary of Diarrhea Treatment Emergent Adverse Events Leading to Dose Reduction
	Summary of Anti-diarrheal Medications
Laboratory	Mean and Mean Change from Baseline in Numeric Laboratory Data: Hematology/ Clinical Chemistry/Urinalysis
	Frequency Table of Potentially Clinically Significant Laboratory Data: Hematology/ Clinical Chemistry/Urinalysis

Grouping	Title
	Shift from Baseline in Laboratory Data: Hematology/ Clinical Chemistry/Urinalysis
Vital Signs	Mean and Mean Change from Baseline in of Vital Signs Data
	Frequency Table of Potentially Clinically Significant Vital Signs Data
	Mean and Mean Change from Baseline in ECG Data
Physical Exam	Summary of Physical Examination
ECG	Frequency Table of Potentially Clinically Significant Values in QTc(F) Interval at Post First Dose
	Frequency Table of Potentially Clinically Significant Values in QTc(B) Interval at Post First Dose
	Frequency Table of Potentially Clinically Significant Values in QT Interval at Post First Dose
LVEF	Mean and Mean Change from baseline in LVEF Data

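### SAP 9.4 tabulates laboratory shifts only as normal versus abnormal, so worsening to Grade 3-4 from an abnormal baseline reads as no shift in that table

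*Protocol*

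**What the plan says.** Protocol 12.4.3 promises mean change by visit, a summary of on-study abnormalities, and shifts: "Shifts in laboratory test values will also be summarized". It does not say how shifts are categorised. SAP 9.4 does: "Shifts in normal/abnormal status between baseline and subsequent visits will be summarized as well". The entry in SAP 12 is titled "Shift from Baseline in Laboratory Data: Hematology/ Clinical Chemistry/Urinalysis" and adds no grade. The SAP states CTCAE grading for adverse events (9.3) but not for laboratory values, and the supplemental SAP does not touch laboratory data.

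Exclusion criterion 8 (Protocol synopsis and 5.2) sets these entry limits, beyond which a patient is excluded:

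- AST and/or ALT: ">3 x institutional ULN (>5 x ULN if liver metastases are present"
- Total bilirubin: ">1.5 x institutional upper limit of normal (ULN"
- Hemoglobin: "<8 g/dL (transfusions allowed"

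Values between the normal range and these limits are therefore eligible. Protocol Appendix 2, Table A2.4, anticipates this by giving separate instructions for patients whose ALT is already Grade 2 at baseline because of liver metastases. Its dose-adjustment rows are set by grade, for example "Grade 3 ALT (>5-20 x ULN) or Grade 3 bilirubin (>3-10 x ULN".

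**The concern.** Liver and blood toxicity govern dose holds and discontinuations in both arms, and Appendix 2 works by grade. The laboratory shift table uses neither baseline grade nor on-study grade. It cannot show severe worsening in a patient who was already abnormal at entry. Among patients who were normal, it cannot separate a trivial excursion from a life-threatening one. Patients with liver metastases or existing anemia are those in whom an arm difference in severe worsening would matter most, and the shift table says least about them.

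**Working it through.** The plan gives no figure to reproduce. The main check places values that eligibility allows first into the two states of SAP 9.4 and then into the grade bands of Appendix 2.

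**Grade bands used.** ALT: Grade 3 is >5-20 x ULN and Grade 4 is >20 x ULN (Table A2.4). Bilirubin: Grade 1 is up to 1.5 x ULN and Grade 3 is >3-10 x ULN (Table A2.11; Table A2.4 gives the same Grade 3 band). Hemoglobin: Grade 3 is <8 g/dL, and Grade 4 is defined by clinical consequences, not by a value (Table A2.6).

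**Classification (illustrative values).**

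| Test | Baseline to worst | SAP 9.4 | By grade |
|---|---|---|---|
| ALT, liver metastases | 4 to 25 x ULN | abnormal to abnormal | Grade 2 to Grade 4 |
| Bilirubin | 1.4 to 4 x ULN | abnormal to abnormal | Grade 1 to Grade 3 |
| Hemoglobin | 9 to 7.5 g/dL | abnormal to abnormal | below Grade 3 to Grade 3 |

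A patient abnormal at entry has only two possible outcomes in a two-state table: still abnormal (no shift) or normal (improvement). Worsening in the same direction always lands in the first. For a patient normal at entry, ALT just above ULN and ALT of 25 x ULN both read as normal to abnormal.

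**Which tests are affected.** For the liver tests the masking does not depend on local ranges, because the limits are multiples of ULN. For hemoglobin it needs only a laboratory lower limit above 8 g/dL. For neutrophils (entry at or above 1.5 x 10^9/L) and platelets (at or above 100 x 10^9/L) it arises only where the laboratory's lower limit is higher than the entry limit. With a neutrophil lower limit of 1.5, no abnormal baseline is admitted. With a lower limit of 2.0, values from 1.5 to 2.0 are. The documents give no normal ranges.

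**Illustrative size.** Let p be the share of patients abnormal at baseline and RR their relative risk of reaching Grade 3-4. The share of Grade 3-4 events that falls in the abnormal-to-abnormal cell is p x RR / (p x RR + 1 - p). Both inputs are assumptions.

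- p = 0.3, RR = 1: 0.3 / (0.3 + 0.7) = 0.30
- p = 0.3, RR = 2: 0.6 / (0.6 + 0.7) = 0.46
- p = 0.5, RR = 1: 0.5 / (0.5 + 0.5) = 0.50
- p = 0.5, RR = 2: 1.0 / (1.0 + 0.5) = 0.67

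These are shares masked in one table, not shares missing from the safety report.

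**Unscheduled results.** Scheduled chemistry and hematology from Cycle 2 onward fall on Day 1, after the capecitabine-free Days 15-21. Appendix 2 expects that Grade 3-4 hematologic values may be found on unscheduled tests. SAP 9.4 does not say whether unscheduled results enter its tables.

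**The case against.** The strongest reply is that severe laboratory toxicity will be reported elsewhere, and much of that is right.

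- **Adverse events.** A reader might infer from a criterion such as "Test result is associated with accompanying symptoms, and/or" that asymptomatic results escape AE reporting. They do not. Protocol 13.1.2 also counts results that need further diagnostic tests or intervention, change dosing, lead to a serious outcome, or are judged to be AEs by the investigator or sponsor. Appendix 2 calls for a hold or discontinuation at many Grade 3-4 values, so many become reportable. Worsening of an existing abnormality qualifies as a TEAE, and Grade 3 or higher TEAEs are tabulated by arm (SAP 9.3).
- **Liver peaks.** SAP 9.5.5 plans plots or tables of on-therapy peak bilirubin against peak AST or ALT, plus a listing of potential Hy's Law cases. An ALT of 25 x ULN would be visible there.
- **Other laboratory output.** The frequency table of clinically significant values does not condition on baseline, so an abnormal baseline does not hide an extreme value. The by-visit statistics include minimum and maximum (SAP 3) and cover both actual value and change.

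These outputs rule out any claim that the events disappear. They do not replace a graded shift. The AE route depends on investigator reporting in an open-label trial. The liver triggers in Tables A2.4 and A2.11 are also worded differently for the two arms, although the general toxicity rules may narrow that difference. The threshold for clinically significant values is not defined. The Hy's Law output covers liver tests only and is not related to baseline: a patient entering at ALT 4 x ULN already meets its transaminase part. Mean changes dilute rare severe events.

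**Conclusion.** The point holds for the shift table defined in SAP 9.4. Worsening to Grade 3-4 from an abnormal baseline is always recorded there as no shift, severity is merged for patients normal at baseline, and no planned table in either SAP crosses baseline grade with worst grade. For the liver tests this follows from the stated definition and entry limits alone. For hemoglobin it needs a lower limit above 8 g/dL. For neutrophils and platelets it depends on local ranges.

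Two stronger readings are not supported. A reader might conclude that severe liver or blood toxicity in these patients would go unreported, but the TEAE tables, the clinically significant value table and the peak liver outputs would show much of it. A reader might also fault Protocol 12.4.3, but that section is silent on categories and is compatible with graded shifts.

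The 30 to 67% range rests on assumed prevalence and risk and is only a guide. No efficacy endpoint or error rate is affected. Severity is minor to moderate: a weakness in safety reporting that is cheap to remove.

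**What to change.** In SAP 9.4, for ALT, AST, bilirubin, hemoglobin, neutrophils and platelets, replace the normal/abnormal shift with a table of baseline CTCAE grade by worst on-treatment grade, by arm. Include scheduled and unscheduled results, and report the proportion worsening to Grade 3 or higher. State the on-treatment window. If it is the TEAE window (to 28 days after last dose), the time after the discontinuation visit will contribute unscheduled results only. Note that a hemoglobin grade derived from the value alone stops at Grade 3, because Grade 4 is defined clinically. Keep normal/abnormal shifts for tests without CTCAE grades, and amend the table title in SAP 12 to match. Defining clinically significant for laboratory values in the same edit would make the companion frequency table interpretable.

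Protocol 12.4.3 need not change. The cost is a paragraph of SAP text and one programmed table per parameter from data already collected. No new samples or procedures are needed.

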12.5 Other Analyses

12.5.1 PK analysis

A population PK study, with sparse sampling at a subset of study sites, will be included in the study to assess the variability of neratinib concentrations when administered in combination with capecitabine among individuals in the target patient population. Blood samples will be collected as specified in [Appendix 1](#), and they will be processed and stored until analysis.

Concentrations of neratinib will be measured in plasma with a validated assay method. NONMEM, a statistical software program that uses non-linear, mixed effects models to determine PK parameters (clearance and volume of distribution), the inter- and intra-patient variability and the population variability in the parameter estimates will be used for this analysis. Random sources of error, intrinsic factors (e.g., age, sex, race, body weight, liver function and renal function) and extrinsic factors (e.g., capecitabine, diarrhea frequency, smoking status) will be evaluated to identify factors that contribute to the observed variability in the PK parameter estimates.

The concentrations in this study will be used in the development of a structural model, and it will include results from other neratinib studies that included intensive sampling. The best model will be evaluated by goodness of fit statistics, reduction in the objective function and posterior predictive checks.

A population pharmacokinetic-pharmacodynamic analysis of neratinib efficacy and tolerability endpoints will be performed in this patient population. The final PK model will be used to generate post-hoc neratinib patient-level plasma PK profiles, from which patient-level neratinib area under the curve (AUC) and maximum plasma concentration (C_{\max}) exposure metrics will be estimated. Neratinib dose and estimated AUC and C_{\max} exposure metrics will then be used to complete an exploratory data analysis of potential exposure-response relationships for efficacy and safety endpoints.

12.5.2 Health Outcomes Assessments

Health outcomes assessments will include the EORTC QLQ-C30, EORTC QLQ-BR23 and the EQ-5D-5L. Questionnaires will be completed by patients at time points specified in [Appendix 1](#).

12.6 Interim Analyses

No interim PFS analysis for early stopping is planned. An interim OS analysis will be performed at the time of final PFS analysis.

The Lan-DeMets alpha spending function approach will be used to adjust the O'Brien-Fleming boundary if the timing based on the final PFS analysis does not correspond to the expected information time of half of the OS events (DeMets and Gordon Lan 1994; Cook 2003).

The hazard rate in the control arm for survival will be assessed to determine if the sample size or duration of follow-up or both should be adjusted to ensure timely achievement of the required 378 death events.

12.7 Determination of Sample Size

The co-primary endpoints will be analyzed using an overall Type I error rate of 0.01 for PFS and 0.04 for OS. To detect a hazard ratio (control versus treatment) of 0.70 with approximately 85% power, 419 PFS events (PD/deaths) are required to be observed; this assumes a median (ITT) PFS of 8.0 months (34.7 weeks) for the experimental arm (neratinib plus capecitabine) and 5.6 months (24.3 weeks) for the control arm (lapatinib plus capecitabine). It is expected that the 419th event will be observed at approximately 26 months after the first patient is enrolled, which would correspond to approximately half of the death events needed to be observed. At this time, an interim analysis on OS will also be performed. For the OS endpoint, a group sequential method will be employed to maintain the overall Type I error rate at 0.04. Specifically, O'Brien-Fleming boundaries will be calculated to create appropriate critical values to which the log rank statistic will be compared.

Information Fraction	Expected Death Events	Study Month	Boundary (Reject H ₀)	Significance Level
50%	185	26	3.066	0.002
100%	378	50	2.058	0.038

These boundaries are designed to detect a hazard ratio (control versus treatment) of 0.725 with approximately 85% power. Overall, 378 events (deaths) are required to be observed; this assumes a median (ITT) OS of 30.3 months for the experimental arm (neratinib plus capecitabine) and 22.0 months for the control arm (lapatinib plus capecitabine). Approximately 600 patients will be enrolled and randomized equally between the two treatment arms.

13 SAFETY DATA COLLECTION, RECORDING AND REPORTING

All observed or volunteered AEs regardless of treatment group or causal relationship to investigational product will be recorded on the AE page(s) of the CRF.

13.1 Definitions

13.1.1 Adverse Events

An AE is any untoward medical occurrence that occurs in a patient or clinical investigation patient administered a pharmaceutical product, and which does not necessarily have to have a causal relationship with this treatment. An AE can therefore be any unfavorable and unintended sign (including abnormal laboratory finding), symptom, or disease temporally associated with the use of an investigational product, whether or not considered related to the medicinal product (definition per International Conference on Harmonisation [ICH] E2A and E6 R1).

All AEs, regardless of seriousness, severity, or presumed relationship to study therapy, must be recorded using medical terminology on the AE CRF page. Whenever possible, diagnoses should be given when signs and symptoms are due to a common etiology (e.g., cough, runny nose, sneezing, sore throat, and head congestion should be reported as “upper respiratory infection”). All measures required for AE management must be recorded in the source document and reported according to Sponsor instructions.

For all AEs, the Investigator must pursue and obtain information adequate to both determine the outcome of the AE and to assess whether it meets the criteria for classification as a SAE (see Section on SAEs) requiring immediate notification to the Sponsor or its designated representative. For all AEs, sufficient information should be obtained by the Investigator to determine the causality of the AE.

Interventions for pretreatment conditions (e.g., elective cosmetic surgery) or medical procedures that were planned before study enrollment are not considered AE.

TEAEs are those events that occur or worsen on or after first dose of investigational product and up to 28 days after the last dose.

13.1.2 Abnormal Laboratory Results

The criteria for determining whether an abnormal laboratory test result should be reported as an AE are as follows:

- Test result is associated with accompanying symptoms, and/or,

- Test result requires additional diagnostic testing or medical/surgical intervention (merely repeating an abnormal test, in the absence of any of the above conditions, does not meet criteria for reporting and an AE), and/or
- Test result leads to a change in study dosing or discontinuation from the study, significant additional concomitant drug treatment or other therapy, and/or
- Test result leads to any of the outcomes included in the definition of a SAE, and/or,
- Test result is considered to be an AE by the Investigator or by the Sponsor

Any abnormal test result that is determined to be an error does not require reporting as an AE, even if it did meet one of the above criteria except for when the test result leads to any of the outcomes included in the definition of a SAE. Clinically significant laboratory results must be recorded in the patient's CRF.

13.1.3 Serious Adverse Events

An SAE is defined as any untoward medical occurrence that at any dose (ICH E2A and E6 R1):

- Results in death.
- Is life-threatening.
This means that the patient is at risk of death at the time of the event; it does not mean that the event hypothetically might have caused death if it were more severe.
- Requires inpatient hospitalization or prolongation of existing hospitalization.
- Results in persistent or significant disability or incapacity.
- Is a congenital anomaly or birth defect.

Medical and scientific judgment should be exercised in deciding whether expedited reporting is appropriate in other situations, such as important medical event(s) that may not be immediately life-threatening or result in death or hospitalization but that may jeopardize the patient or require intervention to prevent one of the other outcomes listed in the definition above. These should also usually be considered serious. Examples of such events are intensive treatment in an emergency room or at home for allergic bronchospasm; blood dyscrasias or convulsions that do not result in hospitalization; or development of drug dependency or drug abuse.

Disease progression should not be recorded as an AE or SAE term; instead, signs and symptoms of clinical sequelae resulting from disease progression will be reported if they fulfill the SAE definition.

